6.3 Infant/child withdrawals and losses to follow up

6.3.1 Withdrawal of consent

The parent/legal guardian is free to withdraw their infant from the study at any time upon request. Withdrawing from the study will not affect their or their infant’s relationship with, or care by, the hospital and affiliated healthcare professionals. A dedicated CRF page in REDCap will be used to capture the date of withdrawal of consent and, if provided, the reason, noting that participants themselves do not need to provide a specific reason for withdrawing. Upon notification of a study withdrawal, the study team should complete the ‘End of Study’ CRF within the BLUEPRINT REDCap DMS which will include reasons for withdrawal.

Withdrawal from the study does not indicate refusal to use existing data already collected unless the parent/legal guardian specifically informs the study team that they withdraw consent for the collection of their infant’s medical, imaging and plasma data. Following withdrawal, subsequent data will only be collected if explicit permission is provided by the parent/legal guardian.

Any infant may be permanently discontinued from study participation for any of the following reasons listed below:

- They are found to have conditions listed in the exclusion criteria during the course of the study
- Withdrawal of consent from study at any time by their parent/legal guardian
- Investigator determines it is in the best interest of the infant

In these cases, the infant will either be replaced in the study cohort or moved into the follow-up phase of the study until withdrawal of consent, death or study close out.

The procedures following the withdrawal or discontinuation of a study infant are outlined in the Manual of Operating Procedures.

Every effort should be made to obtain information on infants who withdraw from the study. An excessive rate of withdrawals can render the study uninterpretable; therefore, unnecessary withdrawal of infants by parent/legal guardian should be avoided. Should a parent/legal guardian decide to withdraw their infant, all efforts will be made to complete and report the observations as thoroughly as possible.

6.3.2 Lost to follow-up

An infant will be considered lost to follow-up if they fail to return for the 1- or 2-year scheduled visits and is unable to be contacted by the study team.

The following actions must be taken if an infant fails to return to the clinic for a required study visit:

- The site will attempt to contact the parent/legal guardian of the infant and reschedule the missed 1- or 2-year follow-up visit and counsel the parent/legal guardian on the importance of maintaining the study visit schedule and ascertain if their infant should continue in the study.
- Before an infant is deemed lost to follow-up, the Site PI or designee will make every effort to regain contact with the infant's parent/legal guardian. Where possible, a minimum of 3 attempts to contact the family will be documented and may include telephone call and/or email and, if necessary, a certified letter to the parent/legal guardian's last known mailing address or local equivalent methods.

Should they continue to be unreachable, they will be considered to have withdrawn from the study, with a primary reason of lost to follow-up.

6.3.3 Replacements

Infants who are withdrawn from the study by a parent/legal guardian will only be replaced in situations where:

- The infant is subsequently identified as having conditions listed in the exclusion criteria (see Section 4.4.3)

6.3.4 Study Closure

An infant is considered to have completed the study if they have completed all study visits (2-year visit assessment if still alive) as outlined in the Schedule of Assessments.

The study may be extended in duration if recruitment has not proceeded at the expected rate.

The end of the study is defined as completion of the last visit or procedure shown in the Schedule of Assessments in the study at all study sites has occurred and all queries have been answered and data entered ('database locked'). At this stage, the Coordinating PI will ensure that all HRECs and RGOs as well as all regulatory and funding bodies have been notified with an End of Study declaration submitted.

Decisions and recommendation on study closure may be made by:

- BLUEPRINT Data Safety Monitoring Committee (DSMC), or
- Study Sponsor

7 POTENTIAL RISKS RELATED TO STUDY CONDUCT

7.1 Risks to the safety and rights of the study participants

Safety and adverse events will be monitored during the study to ensure timely detection of events that may affect safety or continued participation.

Blood sampling is a common practice in the NICU and low risk. There will be no additional risk related to blood sampling than those associated with routine practice with this procedure. These include the potential risk of infection from capillary and arterial sampling, and pain or discomfort from the use of a

microlancet during capillary sampling. Standard site practices will be followed for all blood sampling and research sampling will be aligned with clinical sampling to minimise the risk exposure. The BLUEPRINT protocol has been designed to utilise proteomic analysis which allows us to yield maximum amount of data from small amounts of blood. The volume of blood required for this research study is very small (0.5ml per sample, two samples per patient) and adds very little to the volume of blood taken from preterm infants as part of their routine care. Many preterm infants may require a blood transfusion during their NICU care, the small volume of blood required for this study is unlikely to contribute any additional risk that the participant will require a blood transfusion or not.

There will be minimal to no excessive handling associated with the LUS and EIT recordings required for this study. Infants will only be repositioned for image acquisition if it is deemed appropriate by the treating clinician and the bedside nurse. The investigators will work closely with the treating clinician and bedside nurse to ensure the safe acquisition of LUS and EIT images. If the infant is deemed too unstable then the infant will not be studied.

7.1.1 Definitions

For this study, the following safety definitions will be observed.

Adverse Event (AE): Any untoward medical occurrence in a human subject, including any abnormal sign (for example, abnormal physical exam or laboratory finding), symptom, or disease, temporally associated with the subject's participation in research, whether or not considered related to the subject's participation in the research.

7.1.2 Specific Protocol-Defined Adverse Events and Serious Adverse Events

It is anticipated that there will be minimal risks involved to the infants and families. However, the BLUEPRINT study population involves critically ill preterm infants that are anticipated to have a high number of AEs. Therefore, **the protocol has designated study-specific AEs that are required to be reported within a certain timeframe.** Table 7a below lists specific protocol-defined AEs and the timeframe within which they are to be reported.

Whilst there will be minimal handling associated with LUS and EIT records, study-specific AEs will be reported by the Investigator and assessed for the severity and relatedness. The potential risk of breeches in skin integrity represents a reportable protocol-defined adverse event, and specific data on skin integrity will be included in the study database, as will questions regarding tolerance of the imaging. Clinical staff and parents will be notified of any potential adverse events related to the study (including breeches of skin integrity).

Table 7a Specific Protocol-Defined AEs:

Adverse Event Definition	Reporting Time Frame
Oxygen requirement of $FiO_2 \geq 20\%$ of baseline for 2 hours or more after any imaging measurement	Within 72 hours after each scheduled lung function assessment
Breach of skin integrity or skin irritation associated with LUS or EIT	Within 24 hours of each scheduled lung function assessment
Apnoea requiring stimulation or other intervention that required the EIT or LUS scan to be terminated	Within 72 hours after each scheduled lung function assessment
Acute oxygen desaturation ($SpO_2 < 90\%$) that required the EIT or LUS scan to be terminated	Within 72 hours after each scheduled lung function assessment

Proven infection (culture or PCR positive)	Within 72 hours of a scheduled assessment involving lung function assessments or plasma measurements
--	---

The AEs outlined in Table 7a occurring in each specified time frame are to be recorded on the AE Form within the BLUEPRINT Study REDCap DMS

Any additional adverse events deemed **related or possibly related** to study assessments or procedures, as evaluated by the site PI, should also be documented on the AE form, and entered in the DMS.

EIT belts will only be allocated to a single infant and cleaned and sterilised (UV) using local site standard operating procedure between imaging assessments to minimise the risk of infection. Cables and hardware will be cleaned as per site operating practices between use. Belts that are damaged, worn or soiled will be replaced.

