6.2.4.1 Electrical Impedance Tomography (EIT)

EIT will be used to measure regional tidal ventilation and aeration patterns using the LuMon EIT system (Sentec AG, Landquart, Switzerland), a standalone monitor. The Neonatal Research Group at the MCRI have been using the Sentec EIT system since 2014 and is familiar with all aspects of use^(22, 28-31). The Sentec EIT system integrates image reconstruction models to known characteristics of the infant chest utilising a customised electrode EIT belt system. EIT signals will be sampled at 48Hz and recorded directly into the hard drive capacity of the EIT hardware (stored as standard of care by date and time within the EIT bedside system and not identifiable patient features). A trained technician from the MCRI Neonatal Research Group will provide the necessary training and equipment (hardware and consumables) at each participating site.

The EIT system measures the regional changes in lung volumes through weak alternating currents applied to the body. These travel along the paths of least resistance through the chest, thereby creating electric potentials at the body surface. These potentials are being measured continuously by electrodes and turned into tomographic images of lung function. The electrodes are contained in a belt-like disposable textile patient interface that is fastened to the infant's thorax (**Figure 6a**).^(32, 33) The Sentec EIT electrode system includes a belt made with a knitted polyamide 6 filament yarn trilobal silver electrode fabric (approved for human use). This fabric surrounds a 0.25 cm deep and 1-2 cm wide soft medical grade padding (to ensure the belt can be applied snugly around the chest to avoid movement, and yet not interfere with normal tidal chest movement). To ensure optimal electrical conductance without the need for adhesive gel electrodes, the belts are lightly coated with standard (warmed) ultrasound gel and then wrapped around the chest at nipple level and secured with a Velcro fastener.

The EIT belt is in sterile packaging and can be left in situ for up to 72 hours and suitable for single use only. Infant handling time during belt application is <1min. PI [name] was involved in the development of this belt system,^(32, 33) and has used this EIT belt system on more than 100 infants at the Royal Children's and Royal Women's Hospitals without complication.

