Once adequate/good signal contact is confirmed, EIT data will be recorded continuously (at 48 frames per second) for 2-5 minutes (if there is unacceptable signal interference or artefact, then the measurement will be repeated if practical). A total of 4 EIT images will be repeated over 2-5 minutes recording blocks. At the end of this period, the measurements will cease and the EIT belt Velcro unfastened and removed at a time that will be least invasive for the infant. EIT imaging will be performed in the supine position to a standardised gravity-dependent plane for comparisons. If the clinical team intend to re-position the infant immediately before or after an EIT recording, additional recordings in prone or lateral position will be made. If the clinical team request EIT monitoring for clinical needs, the system and belt will be kept in place until not required anymore.

Figure 6b An EIT belt in situ on an infant during resuscitative management at birth. EIT belt does not impact provision of clinical care. Reproduced with permission of parents from Ref # (22).

The following links provide a video summary of this process and how the use of EIT monitoring is quick, simple, non-invasive and does not interrupt clinical care (note: these videos are during resuscitative care at birth in a delivery room setting):

<https://doi.org/10.26188/19430372>

<https://doi.org/10.26188/14058608>

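### Section 6.2.4.1 makes the EIT belt single use, while section 7.1.2 has it cleaned, UV-sterilised and put back on the same infant; the two must be reconciled

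*Protocol*

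**What the plan says.** Protocol section 6.2.4.1 calls the belt a "belt-like disposable textile patient interface" and states: "The EIT belt is in sterile packaging and can be left in situ for up to 72 hours and suitable for single use only". It then describes a session. Once the recordings are done, "the measurements will cease and the EIT belt Velcro unfastened and removed at a time that will be least invasive for the infant". The one stated exception is monitoring requested by the clinical team, when the belt stays on until it is no longer needed.

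The paragraph that follows Table 7a in section 7.1.2 sets out belt handling as a way of lowering infection risk: "EIT belts will only be allocated to a single infant and cleaned and sterilised (UV) using local site standard operating procedure between imaging assessments". It adds: "Belts that are damaged, worn or soiled will be replaced".

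Table 5a marks lung imaging as required in hospital at 72 hours, Day 7, Day 14, Day 28 and 36 weeks' postmenstrual age. It is optional at 24 and 48 hours, and is repeated at 1 and 2 years corrected age.

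**The concern.** The two sections tell site staff to do different things with the same item. Cleaning a belt between assessments, and replacing it when its condition is poor, makes sense only if it will be worn again. A disposable belt for single use would be discarded and a new one opened.

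The stake is patient safety and consistent conduct. Section 7.1.2 presents belt handling as an infection-control measure, and the participants are sick, very preterm infants. Up to five sites work from this text, and the cleaning method is left to each site's own procedure. An ethics committee reading the protocol is given two incompatible descriptions of that safeguard.

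**Working it through.** There is no statistical figure to reproduce. The check is a comparison of text, with simple arithmetic on the schedule.

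**1. The instructions side by side**

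| | Section 6.2.4.1 | Section 7.1.2 |
|---|---|---|
| Nature of belt | Disposable, sterile-packed | Assigned to one infant |
| After a session | Taken off; single use only | Cleaned and UV-sterilised for the next assessment |
| When a new belt is opened | Each use | Only poor condition is named as a reason |

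Nothing in the protocol defines single use as single patient, and nothing else links the two sections.

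**2. Could the 72-hour wearing limit reconcile them?** It would do so if one continuous placement could cover several sessions. Section 6.2.4.6 equates Day 7 with 168 hours, so Day 14 is 336 hours and Day 28 is 672 hours. The windows are ±12 hours at 72 hours and Day 7, and ±24 hours at Days 14 and 28.

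- 72 hours to Day 7: 168 − 72 = 96 hours. The shortest gap is (168 − 12) − (72 + 12) = 72 hours, and the longest is (168 + 12) − (72 − 12) = 120 hours.
- Day 7 to Day 14: 336 − 168 = 168 hours. The shortest gap is (336 − 24) − (168 + 12) = 132 hours.
- Day 14 to Day 28: 672 − 336 = 336 hours. The shortest gap is (672 − 24) − (336 + 24) = 288 hours.
- Day 28 to 36 weeks: this depends on gestation. An infant born at 22+0 reaches 26+0 on Day 28, ten weeks before 36+0. An infant born at 31+6 reaches 35+6, one day before 36+0.

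One placement therefore cannot span the first four sessions. At the extreme edge of both windows it could only just reach from the first to the second. For the most mature infants the last two sessions could fall within 72 hours, but section 6.2.4.1 has the belt removed after recording, so continuous wear between sessions is not the planned procedure. The optional 24- and 48-hour sessions could share a placement with the 72-hour session on timing alone, so they are left out of the count.

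**3. Belts per infant, all five required in-hospital sessions attended**

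- Section 6.2.4.1: one belt per session gives 5 belts.
- Section 7.1.2: as few as 1 belt, re-applied 5 − 1 = 4 times.

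The two sections lead to different conduct at every required session after the first.

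**The case against.** The best defence is that single use was meant as single patient, which the allocation of each belt to one infant in section 7.1.2 suggests. That may be the intention, but the text does not say so, and the words disposable and sterile-packed in section 6.2.4.1 point the other way. If it was meant, section 6.2.4.1 still needs correcting.

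A second defence is that practice may be uniform anyway. One central group supplies training, hardware and consumables, and section 6.2.4 promises a manual for each site. This stands in part: nothing shows that some sites would use new belts and others reprocessed ones. It does not remove the conflict in the protocol.

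A reader might go further and infer that skin or infection events could never be traced to a reused belt. The documents do not support that.

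- Table 7a captures these events around each assessment, section 7.1.2 adds skin-integrity data to the database, and section 7.3 requires a causality grade from the site investigator.
- The EIT items in sections 6.2.3 and 6.2.6 name belt size but not belt status. Those lists are not closed, and section 8.2.3 places full variable information in a Data Management Plan that is not shown.
- Neither Table 7a row is specific to the belt. The skin row also covers ultrasound, and the infection row also covers plasma sampling.

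A reader might also multiply four re-applications by 550 infants to obtain a number of sessions at risk. That would assume universal reuse, one belt size from 72 hours to 36 weeks although size depends on gestation and weight, no deaths against the 7% mortality quoted in section 11.1, and no discharge before 36 weeks, which section 6.2.7 anticipates.

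Finally, splitting safety tables by new against reused belt may look natural. Under a reuse rule, first sessions would be new and later ones mostly reused, so the split would largely follow visit number and postnatal age and would not isolate an effect of reuse.

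**Conclusion.** The contradiction is real and stands in the current text. Sections 6.2.4.1 and 7.1.2 cannot both be followed at any required in-hospital session after the first. The difference is five belts against possibly one, re-applied up to four times, for an infant imaged at all five time points.

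That count assumes attendance at all five sessions, removal of the belt after each one, one belt size throughout under section 7.1.2, no replacement for poor condition, and no continued wear at the clinical team's request. The conflict itself does not depend on the exact count.

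The point is limited to device safety and conduct. It leaves the primary outcome, sample size and planned analyses unaffected. It should be corrected because it concerns an infection-control safeguard and the correction is cheap.

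**What to change.** - Reconcile sections 6.2.4.1 and 7.1.2 against the device's approved labelling, and state one belt-handling rule for all sites. Which rule is right is for the sponsor to establish from that labelling.
- State how the 72-hour limit applies under that rule, in particular whether it means one continuous placement or total wearing time.
- If the reconciled rule allows reuse, record the belt's use number on the EIT Image Quality CRF named in section 8.3.3, unless it is already captured there.

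The cost is a wording amendment and, at most, one CRF field. Consumable costs rise only if the reconciled rule calls for more belts than the sponsor has budgeted.

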7.2 Assessing the Severity of an Infant's AE

The Severity (mild, moderate, severe, life threatening or fatal) of an AE will be assessed by an investigator, with the following exception:

- Hospitalisation/extended hospitalisation due to progression of clinical condition will not be considered an AE for the purposes of this study.

7.3 Assessing the Relatedness (Causality) of an Infant's AE to Study Procedures

All adverse events/serious adverse events must have their relationship to the study procedures assessed by the Site PI who evaluates the adverse event based on temporal relationship and clinical judgment. The degree of certainty about causality will be determined using the categories below. In a clinical study, the assessments should always be suspected as potentially contributing to an AE.

The relationship of the event to the study intervention will be assessed as follows:

Degree of Causality	Causal Relationship		Description
1	Unrelated	Unrelated	The AE is clearly NOT related to study procedures
2	Unlikely		The AE is doubtfully related to the study procedures
3	Possible	Related	The AE may be related to the study procedures
4	Probable		The AE is likely related to the study procedures
5	Definite		The AE is clearly related to the study procedures

Preterm birth and subsequent NICU care are associated with many risks including severe morbidity and mortality. Many of these risks overlap with events that would or could be an AE/S due to the study assessments.

7.4 Assessing the Severity of an Infant's AE

The Site PI will be responsible for assessing the severity of an adverse event (AE). The determination of severity for all adverse events should be made by the investigator based upon medical judgment and the severity categories of Grade 1 to 5 as defined below.

Grade	Severity	Description
Grade 1	Mild	Asymptomatic or mild symptoms; clinical or diagnostic observations only; intervention not indicated
Grade 2	Moderate	Moderate; minimal, local, or non-invasive intervention indicated; limiting age-appropriate instrumental activities of daily living (ADL)
Grade 3	Severe	Severe or medically significant but not immediately life-threatening; hospitalisation or prolongation of hospitalisation indicated; disabling; limiting self-care ADL
Grade 4	Life Threatening	Life-threatening consequences: urgent intervention indicated
Grade 5	Fatal	Death related to AE

7.5 Assessing the Expectedness of AEs

An AE that is deemed to be related to study procedures must be assessed to determine whether the event is expected or unexpected in terms of the current known safety profile and risks associated with the study procedure. An AE will be considered unexpected if the nature, severity, or frequency of the event is not consistent with the risk information previously described for the study procedure.

Expected adverse reactions are AEs that are known to occur for the study procedures. Expectedness is assessed based on the awareness of AEs previously observed, not on the basis of what might be anticipated from the properties of the study protocol.

It is the responsibility of the BLUEPRINT Medical Monitors to assess expectedness of all reported AEs for the study.

7.6 Documentations of AEs

For the purposes of this study, the Site PI is responsible for recording all AEs, with the following exceptions:

- Conditions that are present at screening and do not deteriorate will not be considered adverse events.

Adverse events will be reported on the study REDCap Adverse Event Form, the details of each AE will include:

- A description of the AE
- The onset date, duration, date of resolution
- Severity (mild, moderate, severe, life threatening or fatal)

- Any action taken, (e.g., none, any treatment given, follow-up tests administered)
- The outcome (i.e. recovering/resolving, not recovered/not resolved, recovered/resolved, recovered/resolved with sequelae, fatal, unknown)
- The likelihood of the relationship of the AE to the study procedure (unrelated, unlikely to be related, possibly related, probably related, definitely related).

Changes in the severity of an AE will be reported as separate events. AEs characterised as intermittent will be documented for each episode. All AEs will be followed to adequate resolution, where possible.

The BLUEPRINT Manual of Operating Procedures details how to record adverse events.

